5.2.5. Study Completion and Post-Study Treatment

The study will be complete when the last subject (including replacement subjects) completes the final phone visit.

The Investigator must provide follow-up evaluation by phone or by clinic visit for all subjects who are prematurely withdrawn from the study or must refer them for appropriate ongoing care.

6. VISIT SCHEDULE AND ASSESSMENTS

The full assessment schedule is presented just before Section 1 ([Introduction](#)) of this protocol.

6.1. Study Schedule

Study procedures will be performed at three visits: the Screening Visit (may be performed on more than one day), Whole-body [¹⁸F]GTP1 PET Imaging Visit (including check-in procedures), and a Follow-up Phone Call.

6.1.1. Screening Visit

Screening evaluations will occur within 30 days prior to the imaging visit. Before any of the screening evaluations are performed for the specific purpose of this study, the subject must provide informed consent for this study in compliance with Good Clinical Practice (GCP) and IRB requirements. Collection of AE data will begin after the informed consent is signed and will continue until the subject discontinues study participation. The screening procedures listed below will be performed and documented to assess whether a subject meets inclusion/exclusion criteria:

- Inclusion and exclusion criteria will be reviewed.
- A medical history will be taken, and demographics will be recorded.
- Concomitant medication information will be obtained.
- Vital signs will be taken after at least 5 minutes of rest in the sitting position, including systolic and diastolic BP, pulse rate, respiratory rate (RR), and oral temperature.
- A complete physical examination will be performed, including height and weight. Rectal, breast and genital examinations are not required as part of this examination.
- A 12-lead ECG will be performed.
- Blood samples will be collected for clinical chemistry, hematology, HIV, and Hepatitis B and C evaluations.
- Urine sample will be collected for urinalysis, drugs of abuse, alcohol, and cotinine screen.
- Serum pregnancy test, if female of childbearing potential.

6.1.2. Whole-body [¹⁸F]GTP1 PET Imaging Visit

AEs will be continuously monitored during the Whole-body [¹⁸F]GTP1 PET Imaging Visit. All eligible subjects will be admitted to the overnight confinement unit on the day prior to the Whole-body [¹⁸F]GTP1 PET Imaging Visit, which will occur within 30 days of screening. Upon check-in, the following procedures will be performed:

- Urine drug, alcohol, and cotinine screening will be performed.
- A symptom-directed physical will be performed.

- Concomitant medications will be recorded.

On the day of imaging, procedures will be performed to ensure that the subject still meets the eligibility criteria. Prior to imaging the following procedures will be performed:

- Review of inclusion and exclusion criteria.
- Subject weight measurement will be obtained.
- Concomitant medications will be recorded.
- Vital signs will be taken just prior to imaging (after at least 5 minutes of rest in the sitting position), including systolic and diastolic BP, pulse rate, RR, and oral temperature.
- A 12-lead ECG will be performed.
- Blood samples will be collected for clinical chemistry and hematology, and a urine sample will be collected for urinalysis.
- Urine pregnancy test, if female of childbearing potential (which must be confirmed as negative within 24 hours prior to [¹⁸F]GTP1 injection).

The subject will have a venous catheter placed in the forearm for administration of [¹⁸F]GTP1, and the subject will lie supine on the camera in preparation for [¹⁸F]GTP1 administration. [¹⁸F]GTP1 will be administered as a bolus IV injection (See Section 5.2.2 for full details on [¹⁸F]GTP1 administration.). Immediately following [¹⁸F]GTP1 administration, PET acquisition will begin. PET scans will be acquired over approximately 6 hours, and the subject may have two breaks during the scanning period. A CT scan will be performed each time the subject lies on the camera. The following procedures will be performed during PET imaging:

- Vital signs will be taken, including systolic and diastolic BP, pulse rate, and RR (taken after at least 5 minutes of rest in the sitting position), approximately 20, 50, 80, and 120 minutes post-injection of [¹⁸F]GTP1.
- ECG will be taken approximately 25 and 45 minutes post-injection of [¹⁸F]GTP1, and at completion of PET imaging.
- The subject will be asked to void during scheduled breaks in the imaging session. Urine will be collected over a period of up to 6 hours throughout the imaging visit for dosimetry analysis.

At the completion of imaging the following procedures will be performed:

- Vital signs will be taken, including systolic and diastolic BP, pulse rate, RR, and oral body temperature (taken after at least 5 minutes of rest in the sitting position).
- ECG will be taken.
- Blood samples will be collected for clinical chemistry and hematology, and a urine sample will be collected for urinalysis.
- Urine will be collected for dosimetry analysis.

The subject will be discharged after all assessments are complete and the subject has been evaluated for AEs. Subjects who experience an AE will not be discharged until the event has resolved or stabilized.

6.1.3. Safety Follow-up Phone Visit

Subjects will be contacted by phone approximately 4 days (\pm 2 days) after the imaging visit, for evaluation of AEs and concomitant medications. The subject will be interviewed to determine if any new AEs occurred or if there have been any new concomitant medications administered. If new medical symptoms have occurred that require further assessment the subject will be asked to return to the research clinic for further evaluation.

6.2. Whole-body [^{18}F]GTP1 PET Imaging Procedures

Whole-body PET imaging will be performed on a Biograph 6 PET/CT camera acquiring an emission scan for each bed position and a CT scan will be performed each time the subject lies on the camera. Subjects will then receive a bolus IV administration of [^{18}F]GTP1 (See Section 5.2.2 for full details on [^{18}F]GTP1 administration.). Immediately following the [^{18}F]GTP1 administration a series of whole-body PET images from the vertex of the head to the thighs will be obtained over a period of up to 6 hours. The subject will have at least two breaks over a six-hour scanning session.

6.3. Urine Collection for Dosimetry Analysis

Commencing with radiotracer injection, urine collection will be initiated. Standard MIRD assumptions will be incorporated in dosimetry models for determination of radiation absorbed doses to target organs and whole-body. Urine samples collected over the imaging period will be evaluated to measure the excretion of [^{18}F]GTP1 through the urinary tract.

6.4. Safety Evaluations

The Investigators will be responsible for monitoring the safety of the subjects that enter this trial. Safety will be evaluated by assessment of AEs, clinical safety laboratory tests, ECG, and vital signs as outlined in the Schedule of Assessments.

6.4.1. Physical Examination

A complete physical examination will include the examination of general appearance, skin, neck (including thyroid), eyes, ears, nose, throat, lungs, heart, abdomen, back, extremities, musculoskeletal, and neurological. Rectal, breast and genital examinations are not required as part of this examination. A symptom-directed exam will be completed upon admission for the Whole-body [^{18}F]GTP1 Imaging Visit; if the subject has new symptoms, only the systems relevant to the symptoms will be examined.

Information for all physical examinations must be included in the source documentation at the study site and will be recorded. Significant findings that are present prior to injection of [^{18}F]GTP1 will be included in the medical history in the subject's source documents. Significant findings made after injection of [^{18}F]GTP1, which meet the definition of an AE must be recorded as an AE.

6.4.2. Vital Signs

Vital signs include systolic and diastolic BP, RR, oral temperature and pulse rate. Vital signs will be obtained during screening and at the Whole-body [¹⁸F]GTP1 PET Imaging Visit, as outlined in the Schedule of Assessments. Temperature will not be taken while the subject is actively undergoing imaging, to avoid any head movement.

6.4.3. Height and Weight

Height and body weight (in indoor clothing) will be measured at screening, and weight will be recorded again at the Whole-body [¹⁸F]GTP1 PET Imaging Visit.

6.4.4. Laboratory Evaluations

In the case where a laboratory value is outside the reference range at screening, a decision regarding whether the result is of clinical significance or not shall be made by the Investigator and shall be based, in part, upon the nature and degree of the observed abnormality. The assessment may be repeated once (for the purpose of inclusion) and in any case, prior to enrollment/randomization, to rule out laboratory error.

In all cases, the Investigator will document the clinical considerations (ie, result was/was not clinically significant and/or medically relevant) in allowing or disallowing the subject to continue in the study.

Clinically relevant deviations of laboratory test results will be reported as an AE, if the criteria are met. Repeated evaluations are mandatory until normalization of the result(s) or until the change is no longer clinically relevant.

6.4.4.1. Hematology

Hemoglobin, hematocrit, red blood cell count, white blood cell count with differential (absolute count and percentage), and platelet count will be measured.

6.4.4.2. Clinical chemistry

A standard chemistry panel will be obtained including electrolytes, liver function tests and analytes to measure renal function, including albumin, albumin/globulin ratio (calculated), alkaline phosphatase, ALT, AST, bun/creatinine ratio (calculated), calcium, carbon dioxide, chloride, creatinine with GFR estimated, globulin (calculated), glucose, potassium, sodium, total bilirubin, total protein, urea nitrogen.

6.4.4.3. Urinalysis

A midstream urine sample will be obtained, in order to avoid contamination with epithelial cells and sediments, and allow proper assessments, and a standard, semi-quantitative dipstick performed to evaluate for common urinary tract conditions. Urine dipstick will include leukocytes, nitrites, urobilinogen, protein, pH, blood (erythrocytes), specific gravity, ketone, bilirubin and glucose.

6.4.4.4. *Serology*

Subjects will be assessed for HIV, Hepatitis B surface antigen, and Hepatitis C antibody results during screening.

6.4.4.5. *Pregnancy testing*

A serum beta-hCG pregnancy test will be performed at screening for females of childbearing potential. Urine pregnancy testing will be performed for women of childbearing potential within 24 hours prior to the administration of a radioligand using a standard kit.

6.4.5. Electrocardiogram (ECG)

A standard 12 lead ECG will be performed. Interpretation of the tracing must be made by a qualified physician and documented on the ECG section of the case report form (CRF). Each ECG tracing should be labeled with:

- Study number
- Subject NDOB (Name Date of Birth) code
- Subject number
- Date
- Time

All ECG tracings will be kept in the source documents at the study site. Only clinically significant abnormalities will be reported on this page. Clinically significant abnormalities should also be recorded as relevant medical history/current medical condition.

The ECG parameters to be reported in the database will include:

- Date and time of ECG
- Heart rate
- PR interval
- QT interval
- QTc interval
- QTcF interval
- QRS duration

The overall interpretation will be collected with a Yes/No statement to confirm if any clinically significant abnormalities are present which need to be specified further.

Original ECG tracings, appropriately signed, will be archived at study site.

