- ³ Vital signs (systolic and diastolic blood pressure [BP], respiratory rate, and pulse rate) will be obtained after at least 5 minutes of rest in the supine position during screening and at the Whole-body [¹⁸F]GTP1 PET Imaging Visit at the following timepoints: pre-injection and approximately 20, 50, 80, and 120 minutes following injection. Oral body temperature will be obtained during screening and at the Whole-body [¹⁸F]GTP1 PET Imaging Visit at the following timepoints: pre-injection and at the completion of imaging.
- ⁴ Electrocardiogram (ECG) will be obtained during screening and at the Whole-body [¹⁸F]GTP1 PET Imaging Visit at the following timepoints: pre-injection, approximately 25 and 45 minutes following injection, and at the completion of the imaging session.
- ⁵ Safety labs (hematology, blood chemistry and urinalysis) will be obtained during screening and at the Whole-body [¹⁸F]GTP1 PET Imaging Visit at the following timepoints: pre-injection and at the completion of imaging. Serology (HIV and Hepatitis B & C testing) will be performed at screening only. Hematology will include hemoglobin, hematocrit, red blood cell count, white blood cell count with differential (absolute count and percentage), and platelet count. Blood chemistry assessments will include albumin, albumin/globulin ratio (calculated), alkaline phosphatase, alanine transaminase (ALT), aspartate aminotransferase (AST), bun/creatinine ratio (calculated), calcium, carbon dioxide, chloride, creatinine with glomerular filtration rate (GFR) estimated, globulin (calculated), glucose, potassium, sodium, total bilirubin, total protein, urea nitrogen. Urinalysis will include leukocytes, nitrites, urobilinogen, protein, pH, blood (erythrocytes), specific gravity, ketone, bilirubin and glucose
- ⁶ For women of childbearing potential, a serum pregnancy test will be performed during screening. Urine pregnancy test will be done at the Whole-body [¹⁸F]GTP1 PET Imaging Visit. The test will occur within 24 hours prior to the injection of [¹⁸F]GTP1 injection. Women without documentation of non-childbearing potential will also receive pregnancy testing.
- ⁷ Approximately, but not exceeding, 370 MBq (10 mCi) of [¹⁸F]GTP1 will be injected IV by bolus injection.
- ⁸ Urine samples will be collected over the imaging period and at scan completion to measure the excretion of [¹⁸F]GTP1 through the urinary tract.

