9.3. Safety Analysis and Statistics

Safety will be evaluated by the following:

- Incidence and severity of AEs
- Results from measurements of vital signs
- Results from measurements of ECGs
- Physical evaluation
- Results from measurements for parameters of clinical laboratory tests (hematology, clinical chemistry, and urinalysis)

All vital signs, ECG, laboratory and AE data will be listed by subject and visit/time and, if ranges are available, abnormalities will be flagged and brought to the Investigator's attention for review. Summary statistics will be provided by visit/time.

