9.4. Sample Size

The sample size for this study was determined by practical considerations and is not based on statistical power calculations. Up to 6 evaluable subjects (with at least 1 male and 1 female) will complete this study.

While the sample size is small, this should be adequate to determine biodistribution and dosimetry calculations of [¹⁸F]GTP1 in Japanese subjects.

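### The ECG interpretation field in Section 6.4.5 cannot separate a normal tracing from a new rhythm, ectopy, conduction-pattern or ST-T change judged not clinically significant

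*Combined protocol and SAP*

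**What the plan says.** Section 2 names ECG findings among the endpoints for the safety objective. Table 1, footnote 4, schedules a 12-lead ECG at screening and, at the imaging visit, "pre-injection, approximately 25 and 45 minutes following injection, and at the completion of the imaging session".

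Section 6.4.5 sets out what is kept from each tracing:

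- A qualified physician interprets it, and the interpretation is documented on the ECG section of the CRF.
- On that page, however, "Only clinically significant abnormalities will be reported on this page".
- The summary item is binary: "The overall interpretation will be collected with a Yes/No statement to confirm if any clinically significant abnormalities are present". Only those abnormalities are then specified further.
- Separately, "The ECG parameters to be reported in the database will include" the date and time, heart rate, PR, QT, QTc, QTcF and QRS. No significance condition applies to these.
- Signed tracings stay in the source documents at the site.

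Section 9.3 lists all ECG data by subject and visit/time, gives summary statistics by visit/time and, where ranges exist, says that "abnormalities will be flagged and brought to the Investigator's attention for review".

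**The concern.** The study is open-label with no control group, so the comparison of each subject's post-injection tracings with his or her own pre-injection tracing is the main evidence on any ECG effect of the dose. For qualitative features, that comparison needs a record of what the physician saw on each tracing. A Yes/No on clinical significance serves an eligibility decision at screening well enough. Applied unchanged to the post-injection tracings, it merges two readings that a before/after comparison must keep apart: normal, and abnormal but not significant.

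Section 6.4.5 also directs significant abnormalities to medical history or current conditions. That suits a baseline tracing, but it makes no distinction for tracings taken after injection. Section 6.4.1 does make that distinction for physical findings: those present before injection go to medical history, and later ones are recorded as adverse events if they meet the definition.

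At stake is whether the reported safety data can show that a subject with a normal pre-injection ECG developed a new, asymptomatic qualitative change. The plan says in Section 3.2 that safety of this tracer has not been specifically studied in Japanese subjects, so a complete descriptive record is part of what the study is for.

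**Working it through.** No power or precision figure applies: "The sample size for this study was determined by practical considerations and is not based on statistical power calculations". The check is a count of tracings, followed by tracing one type of finding through each route into the data.

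**Count of tracings**

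Inputs: up to 6 evaluable subjects (Section 9.4), and ECG times from Table 1, footnote 4.

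- Per subject: 1 screening + 1 pre-injection + 3 post-injection = 5.
- Whole study, at most: 6 × 5 = 30 tracings, of which 6 × 3 = 18 are post-injection.
- Numeric ECG values per tracing: 6 (heart rate, PR, QT, QTc, QTcF, QRS), so up to 18 × 6 = 108 post-injection values.
- Qualitative information per tracing: 1 binary item.

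Since the plan says up to 6, the number of post-injection tracings is 3n for n subjects. It runs from 3 × 2 = 6 at the smallest n that includes one male and one female to 18 at n = 6.

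**Tracing one finding**

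Take an asymptomatic, untreated change that is first seen after injection, leaves rate and intervals essentially unchanged, and is judged not clinically significant. Examples are isolated ectopic beats or an ST-T change.

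| Route | Rule | Is it captured? |
|---|---|---|
| Yes/No item (6.4.5) | Asks only about clinically significant abnormalities | Coded No, as for a normal tracing |
| Description on ECG page (6.4.5) | Significant abnormalities only | No |
| Numeric parameters (6.4.5) | Rate and intervals, every tracing | No, because the change is not in these quantities |
| Flagging (9.3) | Only where ranges are available | No, because morphology and rhythm have no numeric range |
| Listing (9.3) | Lists the data held | No, because nothing was entered |
| Adverse event (7.1.1) | A test result counts only if it causes signs or symptoms, is considered significant, or requires therapy | Normally no |
| Source documents (6.4.5) | All tracings kept at the site | Yes, but outside the database |

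Now take a post-injection change in rate, PR, QT, QTc, QTcF or QRS, also judged not significant. It is stored as a number, listed by subject and time, and summarised. A conduction change that lengthens PR or widens QRS belongs here too. The gap is therefore confined to features that the six numbers do not carry.

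**Illustration (hypothetical; the documents give no rate for such findings)**

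If one of six subjects had a new non-significant qualitative abnormality after injection, the true count would be 1/6 = 16.7%. The database would show 0/6.

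**Consistency within the protocol**

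- Section 6.4.5 requires the interpretation to be documented on the CRF and then restricts that page to significant abnormalities. Read together, it is unclear where a reading of abnormal but not significant should be written.
- Under Cardiac Rhythm, the grading scale in Appendix 1 places asymptomatic, transient signs that need no treatment at Grade 2. A finding that the scale can grade may thus reach the database only if the reader first calls it clinically significant.

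**The case against.** The strongest reply is that most of the quantitative ECG evidence is untouched. Six parameters are stored for every tracing whatever the Yes/No answer, and Section 9.3 lists and summarises them. This stands. A reader might infer from the Yes/No rule that any change judged not significant drops out of the ECG endpoint, or that the endpoint rests wholly on an unblinded judgement of significance. The documents do not support either reading; only qualitative findings are affected.

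A second reply is that nothing is lost for good. The tracings are kept, they are open to monitoring, and there are at most 30 at one site. This also stands. But retrieval would mean re-reading tracings after the event, and nothing in the plan provides for that. The CRF is not among the documents and may hold more than Section 6.4.5 describes; the point concerns the rule as written.

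A third concerns laboratory values. One might infer that the plan treats them in the opposite way, because Section 6.4.4 documents whether the "result was/was not clinically significant and/or medically relevant". That wording follows a paragraph on out-of-range screening values and serves the decision to let a subject continue. For adverse events, Section 6.4.4 also filters on clinical relevance. The contrast should not be used.

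Finally, materiality is low. The dose is a single microdose of at most 10 µg, Section 3.3 calls the risk of a pharmacological effect minimal and names radiation as the primary risk, and no decision rule depends on ECG morphology. That limits the severity. It does not make the binary item a good record for a named endpoint when the physician's reading has already been made.

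**Conclusion.** The point holds for qualitative ECG findings only. As written, Section 6.4.5 gives a new non-significant change in rhythm, ectopy, conduction pattern or ST-T shape the same code as a normal tracing. Unless it qualifies as an adverse event, it is missing from the database and the listings. Up to 18 post-injection readings are exposed to this. How many would actually be affected cannot be estimated from the documents and may well be none.

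The conclusion assumes that the CRF follows Section 6.4.5 literally and that all scheduled tracings are obtained. If the CRF already carries a full interpretation, what remains is the unclear wording in that section. Severity is minor: a cheap improvement to data capture, with no bearing on the dosimetry objective or on the interval data.

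**What to change.** In Section 6.4.5, replace the Yes/No item and the sentence restricting the page to significant abnormalities with one reading per tracing at three levels: normal; abnormal, not clinically significant; abnormal, clinically significant. Have the finding named at both abnormal levels. This also settles where the physician's interpretation is recorded.

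In Section 9.3, add this reading and the named finding to the by-subject, by-time ECG listing already planned, so that each post-injection reading can be set against the pre-injection one. A shift table is optional; with at most 6 subjects the listing is enough.

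The cost is one changed CRF field with a short description and one added item in an existing listing. No further ECGs or readers are needed, because a physician already interprets each tracing. The downside is a few more non-significant entries in the listing. The change does not remove the reader's judgement, since the same unblinded physician still decides between the two abnormal levels, but it leaves the finding visible whichever level is chosen.
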